dosing strategy using a fixed dose could mitigate some of the potential contributing factors of increased risk while effectively avoiding RBC transfusions. A fixed dose strategy will avoid exposure to high doses entirely and could decrease the cumulative dose exposure. Additionally, by not increasing doses, the occurrence of Hb excursions and rapid Hb rises may be minimized. A fixed dose may also reduce Hb cycling, which may be associated with frequent dose changes, which has been associated with worse outcomes in some observational studies of dialysis patients ([Gilbertson et al, 2008](#); [Weinhandl et al, 2011](#)). A consistent, fixed dosing strategy, without titration, may also simplify therapy for patients and providers, which may potentially improve compliance and minimize dosing errors.

The ability of treatment with a fixed dose to effectively reduce the need for transfusions is unknown. One prospective single arm study designed to use primarily 1 fixed dose of epoetin alfa has suggested that such a strategy can reduce RBC transfusions in anemic ND-CKD patients ([Provenzano et al, 2004](#)). During the short 16-week study, 3.7% of patients were transfused compared to 11.1% of patients within 6 months prior to enrollment. However, this study enabled the “fixed dose” to be increased or decreased, and less than half the patients were maintained on the original 10,000 unit per week fixed dose of epoetin alfa throughout the study.

This START-CKD study is designed to describe the benefits and potential risks of a new treatment strategy using a fixed dose of darbepoetin alfa. Anemic ND-CKD subjects, without recent ESA use, will be randomly allocated to treatment with a fixed dose of darbepoetin alfa or to treatment with darbepoetin alfa using a Hb-based titration strategy, which has been the conventional dosing strategy. This study will estimate the subject incidence of RBC transfusions (administered as deemed clinically necessary) in each group and the difference in incidence of RBC transfusions between the 2 groups. However, determining a preferred dosing regimen will also be based on multiple considerations, such as cumulative darbepoetin alfa dose, total number of units of transfusions, Hb concentration, Hb-related parameters (eg, Hb variability, excursions, rate of change), and adverse (eg, CV) events. Given these considerations, an estimation approach was chosen for this study.

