Defined as the number and percentage of subjects with a reported event(s). For subjects with multiple reports of the same event during the study, the subject will be counted only once. If a pre-existing condition worsens on or after the first dose of investigational product administered, the event will be counted as if it occurred on the day it worsened. For adverse event tabulations involving relationship to investigational product, the subject is counted in the tabulations if at least 1 occurrence of the event is

related. For adverse event tabulations involving severity, the highest severity of the particular adverse event will be used for each subject.

Hemoglobin

For all Hb-related endpoints, the Hb measured using the point of care device will be used. For Hb measured by the central laboratory, they will only be summarized descriptively by treatment group at each scheduled visit.

Achieved Hb Concentration while Receiving Investigational Product

For each subject, the achieved Hb concentration while receiving IP will be derived using the area under the curve (AUC) method with all Hb measured during the period starting from Week 13 (Study Day 85) to the last dose date will be included in the calculation. The 12 week interval is indicated in the USPI as escalation period.

Post-baseline Hb Concentration Subgroup

Post-baseline Hb concentration subgroup is defined as < 8.0, ≥ 8.0 and < 9.0, ≥ 9.0 and < 9.5, ≥ 9.5 and < 10.0, ≥ 10.0 and ≤ 10.5, > 10.5 and ≤ 11.0, > 11.0 and ≤ 12.0, > 12.0 and ≤ 13.0, > 13.0 g/dL

Hb Rate of Change (ROC)

Only Hb measured on and after Study Day 1 and while the subject is receiving the investigational product will be included in the calculation.

ROC (g/dL per 4 weeks) is calculated using the following equation:

$$\text{ROC (g/dL/4weeks)} = [(\text{Hb at visit X} - \text{Hb at Visit Y}) / (\text{Date of Visit X} - \text{Date of Visit Y})] * 28, \text{ where X and Y are consecutive post-baseline visits.}$$

Time to Reach Hb ≥ 10.0 g/dL

Time from the Study Day 1 to the date the Hb measurement reached ≥ 10.0 g/dL for the first time. Subjects who never reach Hb ≥ 10.0 g/dL will be censored on the last date of IP.

Proportion of Hb measurements ≥ 10.0 g/dL

Proportion of Hb measurements ≥ 10.0 g/dL = the number of Hb measurements ≥ 10.0 g/dL / Total number of Hb measurements. Only Hb measured on or after Study Day 1 and while the subject is receiving the investigational product will be included in the calculation.

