Hb variability

At any study visit, the Hb variability is the intra-subject Hb standard deviation over the prior 6 months. The Hb variability will be calculated at each scheduled visit from Week 25.

Initial Hb Response

Initial Hb response is defined as the change of Hb concentration from baseline at Week 5.

Initial Hb Response Subgroup

Initial Hb response subgroups are defined as the initial Hb response quartiles based on the initial Hb response analysis set subjects ([Section 7.3](#)) from both treatment groups.

Dose

The dose referred in this analysis plan is the darbepoetin alfa dose from the IP administration. The dose from a placebo injection equals zero darbepoetin alfa dose.

Weight-based Dose at Specific Study Visit

The weight-based dose at any time point = Dose in μg at specific study visit / subject's screening weight in kg.

Cumulative Dose at Specific Study Visit

The cumulative dose at specific study visit = sum of all darbepoetin alfa doses received from Study Day 1 through the specific study visit.

Average Cumulative Dose per 4 Week at Specific Study Visit

Average cumulative dose per 4 week at specific study visit is defined as the 4-week equivalent cumulative dose received at specific study visit.

Average Cumulative Weight-adjusted Dose per 4 Week at Specific Study Visit

Average cumulative weight-adjusted dose per 4 week at specific study visit = average cumulative dose per 4 week at specific study visit / the screening weight in kg.

Transfusion Subgroups

Subjects will be categorized into transfusion subgroups based on the number of transfusion events: No transfusion event, one transfusion event, more than 1 transfusion event.

Transfusion subgroup (on-treatment approach) will be defined using the number of transfusion events where the start date of the transfusion event falls within the evaluation period of the on-treatment approach.

Transfusion subgroup (on-study approach) will be defined using the number of transfusion events where the start date of the transfusion event falls within the evaluation period of the on-study approach.

Time to Event Derivation

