10.5.2 Analyses of Secondary Efficacy Endpoint(s)

Total number of units of RBC transfused per subject will be described for each treatment group, and will be analyzed using a negative binomial regression model which will

include the stratification factors used at randomization. As a sensitivity analysis, exposure adjusted event incidence of total number of units RBC transfused will be presented with 95% CI using Chi-square approximation to the Poisson distribution. These analyses will be performed using both on-treatment approach with the full analysis set and on-study approach with all randomized subjects.

Time to first RBC transfusion will be analyzed using both on-treatment approach with the full analysis set and on-study approach with all randomized subjects. It will be analyzed by each treatment group with Kaplan-Meier curves, Kaplan-Meier percentiles and estimates at 6, 12, 18, and 24 months, the number of subjects censored, and the number of subjects transfused. A supportive analysis will be performed using Cox proportional hazards model (Cox, 1972) stratified by the stratification factors used at randomization to evaluate the difference between the treatment groups. The hazard ratio and its corresponding 95% CI will be estimated.

Average achieved Hb concentration while receiving investigational product will be described as average Hb using the area under the curve (AUC) method. The median of the difference in achieved Hb concentration (Hodges–Lehmann estimate) between treatment groups will be calculated and 2-sided 95% confidence limits will be derived by using a nonparametric Wilcoxon rank-sum statistic (Hollander and Wolfe, 1973). As a sensitivity analysis, the above analyses will be repeated excluding Hb concentrations measured within 3 months (84 days) from an RBC transfusion.

Cumulative doses of darbepoetin alfa adjusted for investigation product exposure time (eg, average cumulative darbepoetin alfa dose per 4 week) will also be summarized, and the median of the difference (Hodges–Lehmann estimate) between treatment groups will be calculated and 2-sided 95% confidence limits will be derived by using a nonparametric Wilcoxon rank-sum statistic.

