10.5.3 Analyses of Exploratory Endpoints

The following exploratory endpoints will be summarized by each treatment group using the full analysis set:

- Darbepoetin alfa dose and weight-adjusted dose received at each study visit
- Hb concentration and its subgroup at each study visit
- Hb concentration change from baseline at each study visit
- Time to first Hb concentration ≥ 10.0 g/dL
- Proportion of Hb measurements ≥ 10.0 g/dL
- Hb rate of change in a 4 week interval at each study visit
- Hb variability at each study visit
- Anti-HLA antibodies as measured using panel reacted antibodies (PRA) over time based on both on-treatment and on-study approaches

Anti-HLA antibodies over time will be summarized by the transfusion subgroup (on-treatment approach) and by randomized treatment group using the full analysis set. The summary will be repeated by the transfusion subgroup (on-study approach) and by randomized treatment group using all randomized subjects.

Furthermore, the following Hb-related information will be evaluated and summarized by randomized treatment group using the full analysis set

- At least one Hb < 8.0 g/dL and the proportion of the Hb measurements < 8.0 g/dL
- At least one Hb < 9.0 g/dL and the proportion of the Hb measurements < 9.0 g/dL
- At least one Hb > 11.0 g/dL and the proportion of the Hb measurements > 11.0 g/dL
- At least one Hb > 12.0 g/dL and the proportion of the Hb measurements > 12.0 g/dL
- At least one Hb > 13.0 g/dL and the proportion of the Hb measurements > 13.0 g/dL

Number of days hospitalized will be summarized by treatment group using the on-treatment approach and the full analysis set. As a sensitivity analysis, the number of days hospitalized will also be summarized by treatment group using the on-study approach and all randomized subjects.

Initial Hb response at Week 5 will be summarized by treatment group using initial Hb response analysis set. The following will be summarized by initial Hb-response subgroup and treatment group using the initial Hb response analysis set:

- Hb concentration at each study visit and the achieved Hb
- Darbepoetin alfa dose at each study visit and the cumulative dose

Subjects received ≥ 1 RBC transfusion and time to first RBC transfusion will be descriptively summarized by the initial Hb response subgroup using on-treatment approach.

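### Apart from the achieved-Hb sensitivity analysis and the initial Hb response set, no Hb endpoint handles a recent RBC transfusion

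*SAP*

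**What the plan says.** SAP 6.3 defines the Hb endpoints one by one.

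- **Rate of change:** "Only Hb measured on and after Study Day 1 and while the subject is receiving the investigational product will be included in the calculation".
- **Proportion at or above 10.0 g/dL:** "Only Hb measured on or after Study Day 1 and while the subject is receiving the investigational product will be included in the calculation".
- **Time to 10.0 g/dL:** "Time from the Study Day 1 to the date the Hb measurement reached ≥ 10.0 g/dL for the first time". Only subjects who never reach it are censored, at the last date of investigational product.
- **Variability:** "At any study visit, the Hb variability is the intra-subject Hb standard deviation over the prior 6 months".

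SAP 10.5.3 adds threshold summaries on the full analysis set, for example "At least one Hb > 11.0 g/dL and the proportion of the Hb measurements > 11.0 g/dL", with the same for below 8, below 9, above 12 and above 13. None of these has a transfusion rule. Transfusion is not a listed reason for ending investigational product (Protocol 8.1), so values after a transfusion stay in.

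Two places do handle transfusion. For achieved Hb, the main analysis uses all values from Week 13 to the last dose, and SAP 10.5.2 then adds: "As a sensitivity analysis, the above analyses will be repeated excluding Hb concentrations measured within 3 months (84 days) from an RBC transfusion". For initial Hb response, SAP 7.3 excludes subjects transfused between randomization and Week 5.

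Protocol 2.3 lists, among the considerations for choosing a preferred regimen, "Hb-related parameters (eg, Hb variability, excursions, rate of change), and adverse (eg, CV) events".

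**The concern.** The SAP accepts that a transfusion can carry over into Hb for 84 days, but acts on it for one endpoint and one analysis set only. Elsewhere, a subject at 9.0 g/dL who is transfused to 10.5 has reached the 10.0 threshold, adds a large value to the rate-of-change distribution, and has a raised standard deviation for the next six months.

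Transfusion is also the primary outcome. If the arms differ in transfusion incidence, they differ in carry-over. The arm that needs more blood could then look better on reaching 10.0 g/dL and worse on high-Hb excursions and variability, for reasons unrelated to darbepoetin dosing. Protocol 2.3 names excursions and rapid rises as suspected contributors to risk, so a reader will look to these tables when weighing the regimens.

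**Working it through.** **The plan's own figures.** SAP 3.2 assumes 25% transfused in each group, with 300 evaluable and 375 enrolled per group. The half-width of the 95% CI for the difference is 1.96 × √(2 × 0.25 × 0.75 / n). This gives 0.0693 at n = 300 (width 13.9%) and 0.0620 at n = 375 (width 12.4%), both within the stated 14%. A 7-point gap equals the stated half-width, so I used 25 ± 3.5, that is 21.5% versus 28.5%.

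**How many values are touched.** Four-weekly visits from Week 1 to Week 97 give 96/4 + 1 = 25 values and 24 intervals. The 84-day window covers 84/28 = 3 visits. With one transfusion per transfused subject:

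- Share of Hb values inside a window: 0.215 × 3/25 = 2.6% versus 0.285 × 3/25 = 3.4%.
- Share of rate-of-change intervals spanning a transfusion: 0.215/24 = 0.9% versus 0.285/24 = 1.2%.

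At 25%, 0.25 × 375 ≈ 94 subjects per arm are transfused. This is an upper bound on the number affected. The primary evaluation period runs to 84 days after the last dose, whereas these Hb summaries stop with investigational product.

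**Between-arm size, by simulation.** The following are assumptions, not from the documents: mean Hb 9.9 g/dL; between- and within-subject SD 0.6; transfusions in the lower half of subjects; Hb at the visit before transfusion at most 8.0; a rise fading to 83%, 50% and 17% at the next three visits. Underlying Hb is the same in both arms, so any all-values gap is carry-over. Gaps are the more-transfused arm minus the other.

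| Measure | Rise 1 g/dL | Rise 2 g/dL | Rise 3 g/dL | After 84-day exclusion |
|---|---|---|---|---|
| Any Hb > 11 (points) | +0.9 | +3.3 | +5.3 | −0.1 |
| Any Hb > 12 (points) | 0.0 | +0.7 | +3.3 | 0.0 |
| Any Hb > 13 (points) | 0.0 | 0.0 | +0.4 | 0.0 |
| Ever Hb ≥ 10 (points) | +0.3 | +0.7 | +0.8 | −0.1 |
| Share of Hb ≥ 10 (points) | +0.2 | +0.4 | +0.5 | +0.2 |
| Intervals with a rise > 2 g/dL per 4 weeks (points) | +0.1 | +0.2 | +0.2 | −0.1 |
| Mean intra-subject SD (g/dL) | +0.003 | +0.008 | +0.014 | +0.001 |

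The +0.2 that remains for the share at or above 10 comes from the exclusion itself, because it removes values from subjects whose Hb is low anyway.

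**A second set of assumptions.** With Hb 9.0, SD 0.5, 24 visits, rises of 1 to 2 g/dL and the same 7-point gap, ever reaching 10.0 differs by about +1.8 to +3.6 points. The share at or above 10 differs by +0.1 to +0.4 points, mean SD by less than 0.01 g/dL, and mean rate of change by about 0.000. A transfusion adds a rise and then an equal fall, so the mean cancels and only spread and extremes move.

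**The case against.** The exploratory objective is to describe Hb under each dosing strategy. Hb as actually experienced, transfusions included, is a legitimate description, and transfusion units are weighed alongside it. No hypothesis is tested. This stands, and it is why the all-values tables should remain the main analysis.

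Exclusion also has a price, because it deletes values according to the primary outcome. In the below-8 and below-9 summaries it would remove persistently low values after a transfusion, most often in the arm that fails more, and so flatter that arm. Where bleeding or surgery caused the drop, it can keep the fall and discard the recovery. It can remove about 3 of the 7 values in a six-month SD. This stands too, and limits the remedy to a parallel analysis.

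A reader might infer four stronger things that the documents do not support.

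- **Spurious initial Hb responses.** SAP 7.3 already excludes subjects transfused before Week 5.
- **Achieved Hb fully protected.** Its main analysis includes post-transfusion values; only the sensitivity analysis removes them.
- **Miscounted rapid rises.** No planned table counts them. Rate of change is summarized by visit and plotted as mean ± SE.
- **Very large distortion.** Within a transfused subject, under the second set of assumptions, the chance of any Hb at or above 10.0 in the next three visits goes from 7% to 50–94%. That compares transfused with untransfused windows, not arms. At the planned 25% in both groups, the carry-over would be about balanced.

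**Conclusion.** The gap is real and can be read directly from the SAP. Time to and proportion of Hb at or above 10.0, variability, the spread and extremes of rate of change, and the above-11, above-12 and above-13 summaries include transfusion-raised values, with no sensitivity analysis.

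The between-arm consequence is conditional and mostly small. It needs a difference in transfusion incidence and, for excursions, a rise large enough to cross the threshold. The high-Hb counts are the strongest case, led by any Hb above 11. Ever reaching 10.0 g/dL matters more when underlying Hb is low. All sizes rest on an assumed rise per transfusion and an assumed 7-point gap.

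The tables could mislead on Hb-related parameters. It would be too strong to say that they cannot answer the exploratory objective. This is a cheap improvement to exploratory analyses and does not threaten the trial's main result.

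**What to change.** In SAP 10.5.3, keep the all-values summaries as the main analysis and add:

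1. A sensitivity analysis repeating the proportion at or above 10.0, rate of change, variability, and the above-11, above-12 and above-13 summaries without Hb measured in the 84 days after an RBC transfusion, reusing the 10.5.2 rule. Say explicitly that the window runs after the transfusion. Drop a rate-of-change interval if either end falls in the window, and report how many values remain in each variability window.
2. For time to first Hb at or above 10.0, a version that treats a first RBC transfusion before reaching 10.0 as a competing event.

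Do not apply the exclusion to the below-8 and below-9 summaries. Add the new outputs to SAP 12.1.

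The cost is SAP wording and extra table runs. Transfusions are already recorded throughout the study (Protocol 7.2.6) and SAP 9.3.3 covers incomplete transfusion dates. The analytic cost is fewer Hb values in transfused subjects and an exclusion that conditions on the outcome. The two versions should therefore be shown together, with neither replacing the other.

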7.1.5 Evaluations After End of Investigational Product

Subjects ending investigational product prior to week 97 will be asked to continue to complete scheduled visits and study procedures outlined in [Section 7.1.4](#) for the remainder of the treatment period. At a minimum, subjects must be followed for the collection of RBC transfusions and endpoint data for adjudication. **Refer to [Section 8.1 for additional information](#).** In addition, serum for anti-erythropoietic protein antibody testing will be collected at the scheduled visit that occurs closest to the receipt of the last dose of investigational product. Adverse events and serious adverse events will be collected as described in [Section 9](#).

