8. REMOVAL AND REPLACEMENT OF SUBJECTS

8.1 Removal of Subjects

Subjects have the right to withdraw from the study at any time and for any reason without prejudice to his or her future medical care by the physician or at the institution.

Subjects (or a legally acceptable representative) can decline to continue receiving investigational product at any time during the course of the study. If this occurs, the investigator is to discuss with the subject the appropriate procedures for discontinuation from investigational product and must discuss with the subject the options for continuation of the schedule of assessments and collection of data, including endpoints and adverse events. These subjects, as well as those who have stopped receiving investigational product for other reasons (eg, initiation of dialysis), are encouraged to continue the schedule of study visits. If the subject is unable or unwilling to continue the schedule of visits:

- At a minimum, subjects should be followed for the occurrence of RBC transfusions and collection of endpoint data for adjudication

- The investigator must document the change in schedule of assessments and the level of follow-up the subject is permitting: in person, by telephone/mail, through family/friends, in correspondence/communication with other physicians, and/or from review of the medical records

Withdrawal of consent for a study means that the subject does not wish to receive further investigational treatment and does not wish to or is unable to continue further study participation; subject data up to withdrawal of consent will be included in the analysis of the study, and where permitted, publically available data can be included after withdrawal of consent. The investigator will discuss with the subject appropriate procedures for withdrawal from the study.

Should a subject (or a legally acceptable representative) request or decide to withdraw from the study, all efforts will be made to complete and report the observations as thoroughly as possible up to the date of withdrawal. All information should be reported on the applicable eCRFs.

Reasons for removal from protocol-required investigational product or procedural assessments include:

- subject request to end investigational product administration
- pregnancy in a female subject (report on Pregnancy Notification Worksheet; see [Appendix D](#))
- safety concern (eg, due to an adverse event)
- initiation of dialysis or receipt of a kidney transplant

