- lack of efficacy (eg, need for a commercial ESA regularly)

Reasons for removal of a subject from the study include:

- withdrawal of consent from the study
- death
- lost to follow-up
- administrative decision by Amgen

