9.3.2 Handling of Missing Data

For all time-to-event outcomes, there will be no imputation of data, except incomplete dates. Missing values will not be imputed and no imputation will be done for the AUC calculation. Missing safety endpoints will not be imputed.

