10. STATISTICAL METHODS OF ANALYSIS

10.1 General Principles

Descriptive statistics will be presented for all endpoints by treatment group. For continuous variables, these include number of observations, mean, standard error (SE) and/or standard deviation (SD), median, 25th percentile (Q1), 75th percentile (Q3), minimum and maximum. For categorical variables, the frequency and percentage are presented. For time to event endpoints: Kaplan-Meier curves, Kaplan-Meier percentiles, the number of subjects censored, and the number of subjects with events will be summarized. Confidence intervals will be constructed as 2-sided at the 95% level. Summaries of laboratory data, Hb and dose related parameters, and vital signs will be completed using the full analysis set, limited to measurements obtained while the subject is receiving the investigational product.

For variables that are summarized over time, the actual visit for a subject may not exactly coincide with their targeted scheduling. The visit windows defined in [Appendix A](#) will be used to assign evaluations to a most appropriate nominal visit for analysis and summarization.

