The reason for IP discontinuation will be reviewed to evaluate its relationship and potential impact on the primary endpoint. Time to first RBC transfusion or discontinuing IP due to lack of efficacy using the on-treatment approach will be analyzed by each treatment group with Kaplan-Meier curves, Kaplan-Meier percentiles and estimates at 6, 12, 18, and 24 months, the number of subjects censored, and the number of subjects transfused or discontinuing IP due to lack of efficacy. A supportive analysis will be performed using Cox proportional hazards model (Cox, 1972) stratified by the stratification factors used at randomization to evaluate the difference between the treatment groups. The hazard ratio and its corresponding 95% CI will be estimated.

Other sensitivity analyses may be performed as appropriate.

Additional transfusion related information collected will be summarized descriptively by treatment group using both on-treatment approach and on-study approach. These include the transfusion setting, and the clinical context surrounding transfusions. These summaries will be transfusion event incidence instead of subject incidence.

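### Time to first Hb ≥ 10.0 g/dL is censored whenever study drug stops, including for lack of efficacy; if those who stop are poorer responders, Kaplan-Meier overstates response (minor, exploratory endpoint)

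*SAP*

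**What the plan says.** SAP 6.3 defines the endpoint as the time from Study Day 1 to the first Hb of at least 10.0 g/dL and adds: "Subjects who never reach Hb ≥ 10.0 g/dL will be censored on the last date of IP". It makes no distinction by reason for stopping.

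SAP 10.5.3 lists the endpoint among those covered by this sentence: "The following exploratory endpoints will be summarized by each treatment group using the full analysis set". It names no method. The method comes from SAP 10.1: "For time to event endpoints: Kaplan-Meier curves, Kaplan-Meier percentiles, the number of subjects censored, and the number of subjects with events will be summarized". The same section restricts Hb summaries to measurements taken while the subject is receiving IP. SAP 9.3.2 adds: "For all time-to-event outcomes, there will be no imputation of data, except incomplete dates".

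Protocol 8.1 gives the reasons for removal from IP. They include "initiation of dialysis or receipt of a kidney transplant", safety concerns, subject request and "lack of efficacy (eg, need for a commercial ESA regularly" (closing bracket cut).

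For transfusion, SAP 10.5.1 plans a supportive analysis that counts such a stop as an event: "Time to first RBC transfusion or discontinuing IP due to lack of efficacy using the on-treatment approach". Nothing equivalent is planned for the Hb endpoint.

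**The concern.** Kaplan-Meier treats a subject censored at a given time as having the same future response as the subjects still at risk. A subject whose IP is stopped for lack of efficacy is plausibly one whose Hb was not rising. Censoring that subject removes a likely non-responder from the risk set, and the response rate of those remaining is applied to the missing share. The curve is pushed up, and more so in an arm with more such stops. Two arms with the same true response could then look different, or a real deficit could be partly masked.

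What is at stake is one descriptive Hb summary. The trial tests no hypothesis and will weigh several Hb-related measures in choosing a preferred regimen, so a summary that misleads in a known direction is worth correcting even at exploratory level.

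**Working it through.** The documents give no response rate, response time or stop rate for this endpoint, so there is no figure of the plan to reproduce. All rates below are assumptions. From the documents come the censoring rule, the four-weekly visits (Day 1 to Week 97 is 96 weeks, or 24 intervals) and the planned 375 per arm.

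**1. Stopping related to response**

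A share *q* of subjects can respond, with exponential response time of mean *m* weeks, seen at the next visit. The rest never respond. The assumed 96-week stop probability is 10% in responders and 40% in never-responders. Per 4-week interval:

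- response probability *h* = 1 − exp(−4/*m*)
- retention *a* = 0.90^(1/24) = 0.9956 for responders, *b* = 0.60^(1/24) = 0.9789 for never-responders
- start at R = *q*, N = 1 − *q*, S = 1, CI = 0; at each visit R ← R·*a*, N ← N·*b*, *e* = R·*h*, S ← S·(1 − *e*/(R+N)), CI ← CI + *e*, R ← R − *e*

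First visit for *q* = 0.75, *m* = 24: *h* = 0.1535, R = 0.7467, N = 0.2447, *e* = 0.1146, S = 1 − 0.1146/0.9914 = 0.8844.

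Had nobody stopped, response by 96 weeks is *q*(1 − exp(−96/*m*)), here 0.75 × (1 − exp(−4)) = 73.6%.

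Results after 24 visits, for the middle case and the two that set the range:

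| Able to respond | Mean time (weeks) | 1 − KM | Nobody stopped | Observed cumulative incidence |
|---|---|---|---|---|
| 85% | 12 | 86.5% | 85.0% | 83.7% |
| 75% | 24 | 76.8% | 73.6% | 71.7% |
| 60% | 40 | 58.7% | 54.6% | 52.7% |

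The excess over the nobody-stopped value is 1.5, 3.2 and 4.1 points. The excess over cumulative incidence is 2.8, 5.1 and 6.0 points. The other combinations of 60, 75 or 85% with 12, 24 or 40 weeks lie within these ranges. For scale, the standard error of 73.6% with 375 subjects is √(0.736 × 0.264/375) = 2.3 points.

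**2. The median**

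In the middle case both methods put it at 28 weeks. With 60% able to respond and a mean of 40 weeks, it is 64 weeks by Kaplan-Meier, 80 weeks by cumulative incidence and 72 weeks had nobody stopped.

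**3. Two arms with the same true response**

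In a simpler model 80% of each arm can respond, with probability 0.1 per visit, and only never-responders stop, from the third visit on. True response by the last visit is 0.80 × (1 − 0.9^24) = 73.6% in both arms. Kaplan-Meier gives 74.3% if 2% of the arm stops for lack of efficacy and 78.2% if 10% does, a spurious gap of 3.9 points. Keeping these stops as non-response gives 73.6% in both. With fast response (0.3 per visit), 10% stopping adds only 1.9 points.

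**4. Control: stopping unrelated to response**

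Repeating step 1 for *q* = 0.75, *m* = 24 with a 20% stop probability for everyone gives 1 − KM 73.6% and cumulative incidence 69.7%. With 35% it gives 73.6% and 66.3%. Kaplan-Meier matches the nobody-stopped value of 73.6% both times, so these gaps are not bias.

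**The case against.** The strongest objections, and what stands of each:

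- **A gap between the two curves need not be bias.** A reader might apply the plan's 20% drop-out allowance and infer that Kaplan-Meier overstates response by several points. Step 4 shows that it does not when stopping is unrelated to response. The two curves then answer different questions: response if kept on drug, and response actually achieved on drug. The 20% was also set for the precision of the transfusion estimate, not as a rate of stopping IP. This objection stands in full, and only response-related stopping counts as evidence of bias.
- **Lack of efficacy is not defined as Hb below 10.0 g/dL.** Protocol 8.1 illustrates it by a regular need for commercial ESA. Under Protocol 7.2.5 Hb results are blinded, with alerts only below 8.0 or above 13.0 g/dL. So the link to poor Hb response is plausible but not established.
- **The fixed-dose arm need not have more such stops.** A reader might infer that it will, because only the titration arm can raise the dose. But Protocol 2.3 says the fixed dose was chosen by simulation to give about the same mean Hb. The direction between arms must be left open.
- **Little output is affected.** SAP 12.1 plans one table for this endpoint, and SAP 12.3 plans no figure. SAP 10.5.2 specifies landmark estimates for transfusion but none are specified here.
- **Much of the correction is already available.** With a common 96-week treatment period, events divided by subjects nearly gives the end-of-treatment cumulative incidence. SAP 10.2 tabulates stop reasons by arm. This stands for the final proportion. It does not correct the Kaplan-Meier percentiles, and no planned output links stop reason to Hb response.

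**Conclusion.** The point holds conditionally and is minor. SAP 6.3 censors every non-achiever at IP stop, and SAP 10.1 brings in Kaplan-Meier. If subjects stopping for lack of efficacy respond less well than those who continue, 1 − KM is biased upward, most in the arm with more such stops. Under the assumed 40% versus 10% stopping, the excess at the end of treatment is about 1.5 to 4 points over response had nobody stopped and about 3 to 6 points over observed cumulative incidence. It shrinks if response is early or such stops are few. The median usually moves little, except when few subjects respond.

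The documents do not support the wider inference that the choice of regimen would be distorted. The endpoint is exploratory, with no hazard ratio or test, and the primary result is unaffected. Protocol 2.3 names Hb concentration, variability, excursions and rate of change as considerations, not this endpoint.

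**What to change.** In SAP 6.3 and 10.5.3, treat ending IP before Hb ≥ 10.0 g/dL, for any reason including death, dialysis, transplant and lack of efficacy, as a competing event. Report the Aalen-Johansen cumulative incidence by arm with the times at which 25% and 50% have responded. Keep censoring for subjects who complete the planned treatment period without response or are still on IP at a data cut, and keep the Kaplan-Meier summary as supportive. Between-arm differences with 95% CIs at landmark weeks are optional.

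The same edit should say whether the last date of IP means the date of the last dose or the End of Investigational Product date, which SAP 6.1 defines separately.

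Using Hb after IP ends is not a clean alternative. Protocol 7.1.5 does ask for visits to go on ("Subjects ending investigational product prior to week 97 will be asked to continue to complete scheduled visits and study procedures outlined in" Section 7.1.4), but Protocol 7.2.9 then permits commercial ESAs, so later Hb no longer reflects the assigned strategy alone.

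The cost is one SAP paragraph and a standard procedure, with no new data. The reported response percentages become slightly lower.
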